## 2.2.3. Interleukin-23 as a Therapeutic Target in Crohn's Disease

The contribution of IL-12 and IL-23 in driving the pathophysiology of CD have been explored in genetic and animal model studies. These studies would suggest that IL-23 plays a predominant role in inflammatory bowel disease (IBD) and, indeed, blocking IL-23 alone may be a more effective strategy than blocking both IL-12 and IL-23 (Parrelo et al. 2000).

A number of observations suggest that CD is mediated by IL-12 and/or IL-23, potentially through the Th1 and Th17 pathways they induce (Monteleone et al. 1997; Berrebi et al. 1998; Parrelo et al. 2000). Moreover, the predominant role for IL-23 in CD has been suggested by genomics studies (Duerr et al. 2006; Barrett et al. 2008). The role of IL-23 in driving intestinal inflammation has been shown in several mouse models of IBD (Hue et al. 2006; Uhlig et al. 2006; Elson et al. 2007; Maxwell et al. 2015), and mice with a genetic deletion of the p19 subunit of IL-23 have been shown to be protected in several models of intestinal inflammation (Hue et al. 2006; Kullberg et al. 2006; Yen et al. 2006).

The relative contribution of IL-12 and IL-23 to disease pathology in IBD has been explored in several studies. The results of these studies would indicate that IL-23, but not IL-12, promotes intestinal inflammation (Hue et al. 2006; Kullberg et al. 2006; Uhlig et al. 2006; Yen et al. 2006). Data from murine models of psoriasis demonstrating a protective role in dermatologic

inflammation (Kulig et al. 2016), as well as clinical trials (Blauvelt et al. 2017; Reich et al. 2017a), would imply that IL-12 blockade may actually be counterproductive to the control of intestinal inflammation. These data suggest that the efficacy obtained with IL-12/23p40 blockade may be through the inhibition of IL-23 and provide a strong rationale for inhibiting IL-23 in CD.

#### **2.2.4. IL-23p19 Blockade in Crohn's Disease**

The efficacy of IL-23p19 blockade in CD has been demonstrated in recent Phase 2 studies evaluating the short-term efficacy and safety of 2 different IL-23p19 mAbs, risankizumab and MEDI2070 (Feagan et al. 2017, 2018; Sands et al. 2017). These Phase 2 studies explored a range of doses from 200 mg to 700 mg intravenous (IV) given up to every 4 weeks (Q4W) through up to Week 12 and provide information regarding the short-term dose-response profile of IL-23p19 blockade in patients with moderately to severely CD. The data from these studies showed evidence of improvements in clinical signs and symptoms, reduction in inflammatory disease burden as evaluated by biomarkers, and evidence of endoscopic healing after a typical short-term induction period. It should be noted that although these studies were small, no safety signals were identified relative to placebo through 12 weeks of treatment, and no additional safety signals were seen in open-label extensions of up to 52 weeks of treatment.

#### **2.2.5. Preclinical and Clinical Studies of Mirikizumab**

Mirikizumab binds the IL-23p19 subunit of human IL-23 and prevents binding of IL-23 to the IL-23R, neutralizing the activity of human IL-23 in vitro. Mirikizumab also neutralizes human IL-23 in vivo, ameliorating the development of psoriasis-like skin inflammation in mice following subcutaneous (SC) injection of human IL-23. Mirikizumab does not prevent IL-12 signaling in vitro. **CCI**

A number of clinical studies of mirikizumab have been completed or are currently ongoing in patients with psoriasis, ulcerative colitis (UC), and CD.

##### Clinical Studies in Ulcerative Colitis

Study 16T-MC-AMAC (AMAC) was a Phase 2, placebo-controlled, double-blind clinical trial of mirikizumab in patients with moderate-to-severe UC, for which induction and maintenance results are available. In the 12-week induction period, mirikizumab demonstrated efficacy for both endoscopic as well as symptomatic indices as assessed by multiple measures (Sandborn et al. 2018). Overall adverse event (AE) frequencies were similar for mirikizumab-treated and placebo-treated patients (Sandborn et al. 2018). In the maintenance period through Week 52, mirikizumab demonstrated durable efficacy for both endoscopic as well as symptomatic indices: among patients in clinical remission at Week 12, 61.1% (Q4W) and 38.5% (every 12 weeks [Q12W]) remained in clinical remission at Week 52. There were few serious adverse events (SAEs) and few discontinuations due to AEs over 52 weeks (D'Haens et al. 2019).

The LUCENT Phase 3 clinical development program for mirikizumab includes studies LUCENT-1 (16T-MC-AMAN), LUCENT-2 (16T-MC-AMBG) and LUCENT-3 (16T-MC-AMAP).

- Study 16T-MC-AMAN (AMAN) was a 12-week double-blind, placebo-controlled, Phase 3 induction study of mirikizumab in participants with moderate-to-severe UC who had failed conventional and/or biologic treatments

### **Efficacy results**

A significantly greater proportion of participants treated with mirikizumab achieved clinical remission at Week 12 (Miri: 24.2%; PBO: 13.3% [99.875%CI: 3.2, 19.1]; p=0.00006). Mirikizumab-treated participants achieved all key secondary endpoints including reduced bowel urgency, clinical response, endoscopic remission, symptomatic remission and improvement in endoscopic histologic inflammation. Mirikizumab also reduced symptoms among participants who had previously not responded to or stopped responding to biologic and/or JAK inhibitor therapies.

### **Safety results**

The incidence of treatment-emergent AEs and SAEs among participants treated with mirikizumab was consistent with that of the previous Phase 2 mirikizumab study in UC and other studies with the anti-IL-23p19 antibody class. The frequencies of treatment-emergent AEs in mirikizumab-treated participants were similar to placebo. There were numerically fewer SAEs (Miri: 27 [2.8%], PBO: 17 [5.3%]) and discontinuations due to adverse events (Miri: 15 [1.6%], PBO: 23 [7.2%]) in mirikizumab-treated participants compared to placebo (D'Haens et al. 2022).

- Study 16T-MC-AMBG (AMBG) was a multicenter, randomized, double-blind, parallel-arm placebo-controlled, Phase 3 maintenance study in participants who completed AMAN.

### **Efficacy results**

A statistically higher proportion of participants met the primary endpoint of clinical remission at one year compared to participants who were re-randomized to placebo (p<0.001). All key secondary endpoints were also met (p<0.001), including significantly higher proportions of participants treated with mirikizumab achieving endoscopic remission, corticosteroid-free remission, resolution or near-resolution of bowel urgency, improvement in endoscopic histologic intestinal inflammation and maintenance of remission, and greater reduction from baseline in bowel urgency symptoms at one year compared to placebo.

### **Safety results**

The frequency of SAEs among participants treated with mirikizumab was numerically lower compared to placebo, and the overall safety profile was consistent with that of the previous mirikizumab studies in UC and studies with the anti-IL-23p19 antibody class. The most common TEAEs reported among participants treated with mirikizumab were nasopharyngitis, arthralgia and exacerbation of ulcerative colitis (Lilly 2021).

- 16T-MC-AMAP (AMAP) is a multicenter, open-label extension study to evaluate the long term efficacy and safety of mirikizumab in participants with moderately to severely active UC. This study is ongoing at the time of this writing.

#### Pediatric Ulcerative Colitis Study

Study I6T-MC-AMBU (AMBU) is an ongoing Phase 2, open-label study to evaluate the safety, pharmacokinetics (PK), pharmacodynamics (PD), and clinical response to mirikizumab to establish induction and maintenance doses to evaluate in Phase 3, in children and adolescents with UC, aged 2 to less than 18 years. Study AMBU will include safety data following mirikizumab treatment for at least 1 year.

#### Clinical Studies in Crohn's Disease

Study 16T-MC-AMAG (AMAG) was a Phase 2, placebo-controlled, double-blind clinical trial of mirikizumab in adult patients with active CD. The primary efficacy objective was to test the hypothesis that treatment with mirikizumab is superior to placebo in the proportion of adult patients with endoscopic response at Week 12, defined as a 50% reduction from baseline in Simple Endoscopic Score for Crohn's Disease (SES-CD) score.

At Week 12, endoscopic response was significantly higher by the predefined 2-sided significance level of 0.1 for all mirikizumab groups compared with placebo (200 mg: 25.8%, 8/31, 95% confidence interval [CI], 10.4–41.2,  $P = .079$ ; 600 mg: 37.5%, 12/32, 95% CI, 20.7–54.3,  $P = .003$ ; 1000 mg: 43.8%, 28/64, 95% CI, 31.6–55.9,  $P < .001$ ; PBO: 10.9 %, 7/64, 95% CI, 3.3–18.6). Endoscopic response at Week 52 was 58.5% (24/41) and 58.7% (27/46) in the IV-C and SC groups, respectively. Thus, mirikizumab effectively induced endoscopic response after 12 weeks in participants with moderate-to-severe CD and demonstrated durable efficacy to Week 52.

Frequencies of TEAE in the mirikizumab groups were similar to PBO. Treatment with mirikizumab has shown clinically relevant and consistent treatment effect in reducing or resolving endoscopic inflammation and patient-reported symptoms in participants with moderately to severely active CD. Through Week 52, frequencies of treatment-emergent AEs were similar across all groups. Frequencies of serious AE and discontinuations due to AE were higher in the nonrandomized maintenance cohort. There were no deaths in any study period, and no malignancies or instances of veno-occlusive disease (including pulmonary embolism) reported in the induction or maintenance period of the study (Sands et al. 2021).

#### Pediatric CD Study

- Study PLATFORMPBCRD3001-16T-MC-AMAY is a Phase 3, multicenter, randomized, platform study of p19 inhibition of the IL-23 pathway to establish efficacy in pediatric CD
  - Study I6T-MC-AMAY (AMAY) is an intervention-specific appendix to the Master protocol PLATFORMPBCRD3001-I6T-MC-AMAY and contains unique study elements specific for mirikizumab.

Additional nonclinical and clinical trial data are summarized in the Investigator's Brochure (IB).

### 2.3. Benefit/Risk Assessment

At the time of this benefit/risk assessment, mirikizumab has demonstrated efficacy in blinded, placebo-controlled Phase 2 studies in psoriasis (Reich et al. 2017b), UC (Sandborn et al. 2018; D'Haens et al. 2019) and CD. In the Phase 2 CD study AMAG, treatment with mirikizumab has shown clinically relevant and consistent treatment effect in reducing or resolving endoscopic inflammation and patient-reported symptoms in patients with moderately to severely active CD. Evaluation of unblinded safety data in ongoing studies in psoriasis, UC, and CD with dose regimens of up to 1000 mg IV Q4W for up to 52 weeks and up to 300 mg SC Q4W for up to 104 weeks has shown a safety profile generally consistent with the IL-23 antibody class. Across the ongoing Phase 2 mirikizumab studies, immediate hypersensitivity reactions, including 2 reports of immediate, infusion-related hypersensitivity events consistent with anaphylaxis, have been reported at the onset or during IV infusion of mirikizumab. Such reactions are considered by the sponsor to be related to mirikizumab and hence have been identified as adverse drug reactions (ADRs). The protocol includes specific measures for reducing the incidence and for management of such events including management of study drug infusion rate and observation during and after infusion. Consult the IB for information regarding ADRs and potential risks with mirikizumab.

Patients  $\geq 15$  and  $< 18$  years of age and body weight  $> 40$  kg were selected for the adolescent addendum due to the similarity to the adult population. Specifically, by 15 years of age patients will often have reached sexual maturity and a weight above 40 kg (the weight required for study enrollment) based on available growth chart data (Emmanuel and Bokor 2020; CDC [WWW] 2019) and their immune systems are fully functional (Georgountzou and Papadopoulos 2017). The lower age of 15 years old required for study enrollment represents the onset for the peak age-specific incidence for CD (15 to 30 years of age for peak incidence), and thus is representative of the general adolescent CD population (Ananthakrishnan 2015).

Given both the efficacy and safety data from the Phase 2 adult study in CD and data from other mirikizumab clinical studies completed to date, potential benefit to both adult and adolescent patients receiving mirikizumab in Study AMAM is reasonably anticipated.

Adverse events of special interest (AESIs)—which are not necessarily ADRs but are of special interest based on standard drug registration topics, safety findings from previous studies in development programs, potential risks associated with biologic immunomodulators as noted in product labels and published literature, and comorbidities and risk factors prevalent in the studied populations—are noted in Section 8.3.7 of this protocol. For all AESIs, including hypersensitivity events, the protocol and IB provide monitoring and management guidance to the investigator. In addition, an independent, external data monitoring committee (DMC) will review clinical trial data at prespecified, regular intervals during the study (Appendix 10.1.4). This independent assessment of clinical trial data will contribute to the overall ongoing evaluation and management of potential risks associated with mirikizumab administration.

In summary, the efficacy and safety data from the Phase 2 CD study AMAG support the continued clinical development of mirikizumab as a treatment in both adult and adolescent patients with CD.

More information about the known and expected benefits, risks, SAEs and reasonably anticipated AEs of mirikizumab can be found in the IB.

### 3. Objectives and Endpoints

Participants in the AMAM Adolescent Addendum will be assigned mirikizumab with clinical trial material provided to sites as blinded treatment. This allows the use of the same test article in both the adult study and the adolescent addendum. The primary and secondary efficacy objectives will summarize the data for open-label mirikizumab-treated adolescents and placebo-treated adults from Study AMAM for endpoints collected in both adolescents and adults.

Objectives	Endpoints
Co-Primary	
To evaluate the efficacy of mirikizumab as assessed by 
 
• Clinical response at Week 12 and endoscopic response at Week 52 and
 
• Clinical response at Week 12 and clinical remission at Week 52
 
	The proportion of patients achieving: 
 
• clinical response CCI at Week 12 and endoscopic response by SES-CD at Week 52 and
 
• clinical response CCI at Week 12 and clinical remission CCI at Week 52
 

Secondary	
To evaluate the efficacy of mirikizumab as assessed by 
 
• clinical response CCI and endoscopic response at Week 52
 
• clinical response CCI and clinical remission by CDAI at Week 52
 
	The proportion of patients achieving: 
 
• clinical response CCI and endoscopic response at Week 52
 
• clinical response CCI and clinical remission by CDAI at Week 52
 

• To evaluate the efficacy of treatment with mirikizumab in endoscopic response at Week 12	• Proportion of patients achieving endoscopic response at Week 12
• To evaluate the efficacy of treatment with mirikizumab in endoscopic remission at Week 52	• Proportion of patients achieving endoscopic remission SES-CD $\leq 4^a$ at Week 52
• CCI	• CCI
• To evaluate the efficacy of treatment with mirikizumab in endoscopic remission at Week 12	• Proportion of patients achieving endoscopic remission SES-CD $\leq 4^a$ at Week 12
• To evaluate the efficacy of treatment with mirikizumab in clinical remission	• Proportion of patients achieving clinical remission by CDAI at Week 12

Objectives	Endpoints
by CDAI	
 
Proportion of patients achieving clinical remission by CDAI at Week 52
 


 
To summarize the efficacy of treatment with mirikizumab in clinical remission CCI
 
	
 
Proportion of patients achieving clinical remission CCI
 
Proportion of patients achieving clinical remission CCI
 

 
To summarize the efficacy of treatment with mirikizumab CCI
 
	
Mean change from baseline at Week 12 and at Week 52:
 
 
CCI
 
CCI
 

 
To summarize the efficacy of treatment with mirikizumab CCI
 
	
Change from baseline in the following CCI
 
 
CCI
 
CCI
 

 
To summarize the proportion CCI
 
	
 
Proportion of patients who had CCI
 
Proportion of patients who had CCI
 
Proportion of patients who had CCI
 

 
To evaluate the pharmacokinetic and pharmacokinetic/pharmacodynamic relationships of mirikizumab
 
	
 
CCI
 
CCI
 

 
To summarize the change CCI
 
	
 
Change from baseline CCI
 
Change from baseline CCI
 

 
To summarize the change CCI
 
	
 
Change from baseline CCI
 
Change from baseline CCI
 

 
To summarize the efficacy of treatment with mirikizumab in endoscopic
 
	
 
Proportion of patients achieving endoscopic remission CCI
 

Objectives	Endpoints
CC1	CC1 • Proportion of patients achieving endoscopic remission CCI

EP [REDACTED]

[REDACTED]

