## 9.4. Statistical Analyses

### 9.4.1. General Statistical Considerations

Statistical analysis of this study will be the responsibility of Lilly or its designee. A detailed SAP describing the statistical methodologies will be developed by the sponsor or its designee. SAS (Version 9.2 or higher, SAS Institute, Cary, NC, USA) will be used for the statistical analysis.

Unless otherwise specified, efficacy analyses will be conducted on the mITT population, and safety analyses will be conducted on the safety population as described in Section 9.3.

Statistical analyses will include the following 3 participant cohorts:

1. Mirikizumab-treated adolescents: Adolescent participants in the addendum, ages 15 to less than 18 years old, assigned mirikizumab treatment as specified in Section 4.1.
2. Placebo-treated adults: Adult participants from Study AMAM, ages 18 years and up, assigned placebo treatment as described in Section 4.1.
3. Mirikizumab-treated adults: Adult participants from Study AMAM, ages 18 years and up, assigned mirikizumab treatment as described in Section 4.1.

For both induction and maintenance phases, the efficacy of mirikizumab-treated adolescent patients will be summarized alongside the adult placebo group and the adult mirikizumab group.

When reported, descriptive statistics will include the number of participants; mean, standard deviation, median, minimum, and maximum for continuous measures; and frequency counts and percentages for categorical measures.

Full details of all a priori specified analyses for the amendment will be provided in a separate SAP, specific to the amendment. Any change to the data analysis methods described in the protocol will require an amendment ONLY if it changes a principal feature of the protocol amendment. Any other change to the data analysis methods described in the protocol, and the justification for making the change, will be described in the clinical study report. Additional exploratory analyses of the data will be conducted as deemed appropriate.

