#### **9.4.3.2. Secondary Analyses**

##### **Secondary Endpoints**

Refer to Section 8.1 for definitions of the following endpoints:

- Clinical remission by PRO
- Clinical remission by CDAI
- Endoscopic remission SES-CD  $\leq 4$
- Clinical remission **CCI** [REDACTED]

Confidence intervals for all secondary endpoints will also be provided for adolescents assigned to mirikizumab and adults assigned to placebo treatment and are not intended to correspond to a statistical hypothesis test.

Additional analyses of the secondary efficacy and health outcome endpoints may be considered and will be fully detailed in the SAP. Additional endpoints may be prespecified in the SAP.

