15. Health outcome and efficacy subgroup analyses were removed in Section 5.7.
16. The adolescent PK interim analysis was removed in Section 5.8.2.
17. Endpoint definitions for endpoints no longer needed were removed in Appendix 1 to align with the changes in the objectives and endpoints table.

18. Added RHI and GHAS histology endpoints and definitions of histologic response and remission in Appendix 1.
19. Updated analyses in Appendix 2 to remove endpoints not being summarized and align with changes in objective and endpoints table.
20. Updated Appendix 3 to include details of enrollment stoppage and subsequent changes to analyses.
21. Demographic information changed to be provided in listing instead of summary table in Appendix 4.
22. Updated study intervention compliance in Appendix 5 to align with Study AMAM changes.
23. Added details for what constitutes a specified change to concomitant CD medications in Appendix 9.
24. Added Appendix 10 with details of study visit/week definitions to align with Study AMAM.
25. Updated references and made minor editorial changes to improve clarity and consistency but did not change meaning throughout the document.

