
Measure	Description	Variable	Derivation / Comment / Endpoints	Definition of missing
CDAI	
The CDAI is an 8-item disease activity measure comprised of a composite of 3 patient-reported and 5 physician-reported/laboratory items (physical signs and a laboratory parameter [hematocrit]).
 
Participant responses are summed over a 7-day period and all items are subsequently weighted, yielding a total score range of 0 to 600 points. All endpoints derived using participant responses will be calculated from daily electronic diary data from the most recent 7 days (possibly nonconsecutive) out of the 12 days prior to the day of the visit, after removing the day(s) of the endoscopy prep, the day of endoscopy procedure, and the 2 days following the endoscopy procedure.
 
SF captures the number of liquid or very soft stools.
 
AP score is classified as 0=none, 1=mild, 2=moderate, 3=severe.
	Clinical response by PRO	
Clinical response by PRO is defined as at least a 30% decrease in SF or AP, and no worse than baseline.
 
If <math>[100 * (\text{SF average} - \text{baseline SF average}) / \text{baseline SF average}] \leq -30</math> or <math>[100 * (\text{AP average} - \text{baseline AP average}) / \text{baseline AP average}] \leq -30</math>, and SF average <math>\leq</math> baseline SF average and AP average <math>\leq</math> baseline AP average, then clinical response by PRO is achieved.
	Missing if less than 4 days of data are available at either baseline or endpoint
		CDAI total score Change from baseline in CDAI total score	
CDAI total score is based on the CDAI questionnaire in Appendix 7. It also utilizes the standard weights table in that section.
 
Change from baseline in CDAI score is defined as CDAI score – baseline CDAI score.
	Missing if CDAI total score is missing at endpoint. CDAI total score will be missing if any of its components are missing. If none of the options in section 4 of the CDAI questionnaire is checked, it will be assumed that no extra-intestinal manifestations were present.
		Clinical remission by CDAI	Clinical remission by CDAI is defined as a CDAI total score $< 150$ .	Missing if CDAI total score is missing at endpoint.

Measure	Description	Variable	Derivation / Comment / Endpoints	Definition of missing

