Abbreviations: AP = abdominal pain; CD = Crohn's disease; CDAI = Crohn's Disease Activity Index; CDC = Centers for Disease Control and Prevention; eCRF = electronic case report form; ER = emergency room; ESR = erythrocyte sedimentation rate; CCI [REDACTED]; PRO = patient-reported outcome; CCI [REDACTED] SES-CD = Simple Endoscopic Score for Crohn's Disease; SF = stool frequency.

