## 6.2 Appendix 2: Description of Analyses

Measure	Variable	Analysis Method (Section 5.1.1)	Population (Section 4)	Time Point(s)
Combined Endpoints	Clinical response CCI [REDACTED] at Week 12 and Endoscopic Response at Week 52	Descriptive summaries	mITT	Week 52
	Clinical response CCI [REDACTED] at Week 12 and Clinical Remission by PCDAI at Week 52	Descriptive summaries	mITT	Week 52
SES-CD	Endoscopic Response	Descriptive summaries	mITT	Week 12 Week 52
	Endoscopic remission SES-CD $\leq 4$	Descriptive summaries	mITT	Week 12 Week 52
CCI [REDACTED]	Clinical remission CCI [REDACTED]	Descriptive summaries	mITT	Week 12 Week 52
	Clinical response CCI [REDACTED]	Descriptive summaries	mITT	Week 12 Week 52
Urgency NRS	Urgency NRS score, Change from BL in Urgency NRS Score	Descriptive summaries	mITT	Each applicable visit
Medical resource utilization and health economics	Proportion of participants who had Crohn's related emergency room visits	Descriptive summaries	mITT	Week 52
	Proportion of participants who had Crohn's related hospitalizations	Descriptive summaries	mITT	Week 52
	Proportion of participants who had Crohn's related surgeries	Descriptive summaries	mITT	Week 52
CCI [REDACTED]	CCI [REDACTED]	Descriptive summaries	mITT	Week 12 Week 52
	CCI [REDACTED]	Descriptive summaries	mITT	Week 12 Week 52

Abbreviations: BL = baseline; NRS = Numeric Rating Scale; mITT = modified intent-to-treat population; CCI [REDACTED]

[REDACTED]; SES-CD = Simple Endoscopic Score for Crohn's Disease.

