### 6.3 Appendix 3: Changes to Protocol-Planned Analyses

As compared with the AMAM Adolescent Addendum (15.2), the SAP Version 2 content differs in several respects. The analysis and endpoints describe in the SAP will supersede the language in the protocol.

Due to the early stoppage of enrollment and small number (6) of adolescent participants enrolled, there is limited utility of any comparison to adult participants treated with mirikizumab or placebo from Study AMAM. Thus, no comparisons will be performed. Instead, descriptive summaries will be provided of select key efficacy endpoints. Listings and summaries of safety related endpoints will be provided as well. Details of these listings and summaries are provided in Section 5.

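### Does SAP Version 2 lose clinical remission by CDAI, a protocol secondary endpoint, without saying so?

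*Protocol*

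**What the plan says.** Protocol 15.2, Section 3, names clinical remission by CDAI in three secondary entries. One is "Proportion of patients achieving clinical remission by CDAI at Week 12", the second is its Week 52 counterpart, and the third is a Week 52 composite with clinical response. Section 9.4.3.2 names the endpoint again and adds: "Confidence intervals for all secondary endpoints will also be provided for adolescents assigned to mirikizumab and adults assigned to placebo treatment". Section 9.4.1 says that adolescent efficacy "will be summarized alongside the adult placebo group and the adult mirikizumab group".

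SAP Version 2 keeps the derivation. Appendix 1 has an entry beginning "Clinical remission by CDAI is defined as a CDAI total score", with the cut-off at 150 and a rule for missing values, and Appendix 7 holds the questionnaire and weight tables. The secondary list in SAP Section 1.1 and the table in Appendix 2 show no legible CDAI remission row. Table AMAM.5.2 has one group, the adolescents on mirikizumab.

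On what was removed, item 17 of the SAP version history states: "Endpoint definitions for endpoints no longer needed were removed in Appendix 1 to align with the changes in the objectives and endpoints table". Appendix 3 states: "The analysis and endpoints describe in the SAP will supersede the language in the protocol". It gives the reason as the 6 adolescents enrolled, but it does not itemise the endpoints left out.

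**The concern.** A secondary endpoint in the current protocol has a full derivation in the SAP and no visible analysis. The SAP says that unneeded definitions were deleted, so a definition that survives suggests that the endpoint was meant to be analysed and that its row was lost. Section 5.5 of the SAP marks exploratory analyses as not applicable, so the endpoint was not moved there.

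The abbreviation lists seem to point the same way. The one under Appendix 1 includes "CDAI = Crohn's Disease Activity Index; CDC = Centers for Disease Control and Prevention". The one under Appendix 2, which begins "Abbreviations: BL = baseline; NRS = Numeric Rating Scale; mITT = modified intent-to-treat population", shows no CDAI entry.

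The adult groups raise a parallel question. The protocol commits to descriptive summaries of three cohorts and the SAP shows one. Appendix 3 explains the absence of comparisons, but protocol 15.2 had already replaced comparison with description. SAP Section 1.1 and protocol 9.4.1.2 nevertheless still open by saying that adolescents will be compared with adults on placebo.

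At stake is reporting. Someone checking the results against protocol 15.2 would find secondary endpoints and adult columns absent, and might not know whether that was a decision or an oversight.

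**Working it through.** The plan gives no figure to reproduce here, so the check is mainly a comparison of the two documents.

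**Step 1. Trace the protocol's secondary items through the SAP.**

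| Protocol Section 3, secondary | SAP 1.1 | SAP Appendix 2 | SAP Appendix 1 |
|---|---|---|---|
| CDAI remission, Week 12 | one stand-alone remission index, name blacked out | same | derived |
| CDAI remission, Week 52 | same | same | derived |
| Response with CDAI remission, Week 52 | none legible | not among the two combined rows | component derived |
| Response with endoscopic response, Week 52 | no secondary row legible | no row beyond the co-primaries | components derived |
| PK and PK/PD relationships | none legible | none legible | none legible |

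For CDAI remission the count is 3 protocol entries, 1 derivation, 0 legible analysis rows and 0 named deletions.

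**Step 2. How firm is the absence?** Both rows of the combined block in Appendix 2 are the co-primaries, and the remission row uses PCDAI. The CDAI composite is therefore not in that block. The stand-alone endpoints are less certain, because the index in the remission row is blacked out in both places and one secondary row of SAP 1.1 is wholly redacted. That the blacked-out index is not CDAI is a strong inference, since CDAI is printed openly elsewhere. The abbreviation list adds little. PCDAI is printed in the Appendix 2 table but is not in the visible part of the list either.

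**Step 3. Does the surviving definition show that an analysis was planned?** Appendix 1 also keeps clinical response by PRO, clinical response by CDAI, and the AP and SF averages. None has a legible row of its own in Appendix 2. Unused definitions are a general residue of editing, so the CDAI remission entry carries no special signal.

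**Step 4. Does the SAP declare the trimming?** Yes, in general terms. Item 1 of the version history restricts the objectives to the main efficacy endpoints after enrollment stopped. Item 19 says that endpoints not being summarised were taken out of Appendix 2. Appendix 3 says that the SAP departs from addendum 15.2, takes precedence over it, and summarises a selection of endpoints.

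**Step 5. What would restoring the rows add?** With n = 6 and z = 1.96 (z² = 3.84), the Wilson interval that SAP 5.1.1 names gives:

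- 0/6: upper limit = z²/(n + z²) = 3.84/9.84 = 39.0%, so the width is 39.0 points (the same at 6/6).
- 3/6: half-width = [z/(1 + z²/n)] × √[p(1 − p)/n + z²/(4n²)] = (1.96/1.640) × √(0.0417 + 0.0267) = 0.312. The interval is 18.8% to 81.2%, a width of 62.5 points.

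One participant is 1/6 = 16.7 points. Under Appendix 1 the CDAI total is missing if any component is missing, and nonresponder imputation then counts that participant as a failure. A single missing item could move the proportion by that amount.

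**The case for a change.** The strongest case for a change is that the stated reason does not fit the omission. Appendix 3 argues that comparison with adults is of little use at n = 6. That explains dropping comparisons. It does not explain dropping one adolescent proportion while keeping others of the same size. The derivation is already written, three rows cost almost nothing, and naming the omissions in Appendix 3 would take a few lines.

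Part of this stands. The SAP gives no reason specific to CDAI, and an itemised list would have been better practice. It does not make a case for amending the plan. Adding the rows would reverse a declared choice of endpoints and change no conclusion. Listing the omissions is documentation, and a place for it exists: protocol 9.4.1 and SAP 5.1 both say that changes to the analysis methods which do not alter a principal feature are described, with their justification, in the clinical study report.

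The related points do not add weight:

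- **Clinical remission by PRO.** Protocol 9.4.3.2 lists it, but its definition and time points are redacted, so nothing firm can be said about whether it is missing.
- **Adult columns.** The SAP discloses their removal in Section 1.1 and in items 2 and 7 of the version history, and Table AMAM.5.2 applies it consistently. Leaving them out is a fair trade-off. Readers may over-read 6 adolescents set beside a larger adult trial. A Week 52 placebo column would also need a rule for placebo nonresponders, who move to mirikizumab at Week 12 (protocol 4.1).
- **The leftover comparison wording.** The next paragraph of SAP 1.1 corrects it, and protocol 9.4.1.2 goes on to describe a descriptive summary. It is a clerical slip.

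**Conclusion.** The two documents do differ. Three protocol entries for CDAI remission have no legible analysis in SAP Version 2, and the protocol's three cohorts become one. The likeliest reading is deliberate trimming after enrollment stopped at 6. The SAP announces such trimming in general terms and applies it to other secondary items too. No change to the plan follows. The omitted quantities are descriptive proportions with intervals 39.0 to 62.5 points wide. No hypothesis is tested, and no error rate, co-primary endpoint or safety output depends on them. The study report is already the agreed place to record departures of this kind.

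This rests on two assumptions: that the blacked-out remission index in the SAP is not CDAI, and that the omission was intended. If the index is CDAI, the two stand-alone endpoints are in the plan after all and only the composite is missing. If the omission was an oversight, three imprecise descriptive rows are lost, which would be a gap in completeness and would alter no conclusion about the drug.
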